12.6 Product Complaint Reporting

In geographies where devices are market-released, product complaint reporting is applicable. This includes when an AE is related to a market-released device during the study. The reporting of product complaints is not part of the clinical study and should be done in addition to the Adverse Event and Device Deficiency reporting requirements. Refer to local regulations for reporting requirements.

Product Complaint: Any written, electronic or oral communication that alleges deficiencies related to the identity, quality, durability, reliability, safety, effectiveness or performance of a medical device that has been placed on the market.

It is the responsibility of the Investigator to report all product complaint(s) associated with a medical device distributed by the Sponsor, regardless whether they are related to intended use, misuse or abuse of the product. Reporting must be done immediately and via the regular channels for market-released products.

The reporting of product complaints by the clinical team must be done according to the local Standard Operating Procedures. The Sponsor will notify the regulatory authorities (e.g. FDA) as applicable for the following incidents immediately upon learning of them:

- Any malfunction or deterioration in the characteristics and/or performance of a device, as well as any inadequacy in the labeling or instructions for use which led or might have led to the death or serious deterioration in the state of health of a patient, user, or other person.
- Any technical or medical reason resulting in withdrawal of a device from the market by the manufacturer.
- A serious deterioration in the state of health includes:
 - Life-threatening illness or injury.
 - Permanent impairment of a body function or permanent damage to a body structure.
 - A condition necessitating medical or surgical intervention to prevent permanent impairment of a body function or permanent damage to a body structure.

13. Data Review Committees

13.1 Data Safety Monitoring Board

The purpose of the Data Safety Monitoring Board (DSMB) is to conduct unbiased review of all safety data in comparison to the established criteria in order to determine if the rate of SAEs is acceptable, to evaluate interim data analysis results, to provide related advice on study management and progress and to make any recommendations regarding the study protocol. Members of the DSMB will be comprised of three (3) voting individuals with relevant expertise for the study and a biostatistician; they will not be

employees or shareholders of the Sponsor and they will not be a participating DIAMOND-AF II Investigator.

The DSMB will be responsible to communicate any safety concerns, scientific concerns or other perceived concerns to the Sponsor or designee as soon as possible. The DSMB will provide, after each scheduled meeting, written recommendation regarding the continuation of the trial, early stopping or suggested changes for the conduct of the trial. The Sponsor is responsible for informing the IRB/EC and regulatory authorities, as applicable, if the DSMB has advised them of any major safety concerns and has recommended the study be stopped or if they have made any recommendations to alter the study. DSMB decisions are final and non-negotiable by the sites.

13.2 Clinical Events Committee

The purpose of the Clinical Events Committee (CEC) is to complete unbiased reviews and classification of SAEs and deaths reported by clinical study investigators. The CEC will consist of physicians who are not participating Investigators in the DIAMOND-AF II Study and who do not have any significant investment in the Sponsor or any of their entities. The three (3) voting members who serve on the CEC to provide independent, unbiased review and adjudication of clinical events throughout the trial will also be DSMB members. A complete description of CEC and DSMB responsibilities, qualifications, members and operating principles will be outlined in a combined charter.

13.3 CRO/Core Lab(s)

A designated contract research organization (CRO) will provide centers and/or subjects with instructions and training on the use of an event monitors that serves as a hand-held event recorder for short duration recordings and 24 hour Holter monitors.

Subjects will be provided with an event monitor prior to discharge from the hospital and instructed to collect 1-minute ECG recordings with their event monitor if they experience AF symptoms throughout the study. Additionally, subjects will be required to collect 1-minute ECG recordings with their event monitor two times per month starting at the end of the blanking period to the 12-month follow up visit. Recordings made due to symptomatic episodes during the effectiveness evaluation period may count towards the scheduled, required monthly recordings.

The event monitors will be configured to automatically transmit recordings securely and wirelessly to the Core Lab. All events will be analyzed by the Core Lab to determine arrhythmia recurrence. The company will identify the subject's transmitted rhythm and send reports to the investigational center within 72 hours. If there is discordance between the Core Lab's rhythm analysis in the report and the Investigator, a third-party cardiologist will be used for final rhythm determination. All event monitors should be returned to the Core Lab after a subject completes the study.

Subjects will be provided instructions on how to collect a 24 hour Holter reading with the event monitor provided for event monitoring during the 3, 6 and 12 months post-ablation procedure follow-up visit windows.

The Core Lab will review, analyze and report on all event and Holter recordings as well as the 12-lead ECGs taken at the 3, 6 and 12-month follow-up visits.

14. Statistical Design and Methods

Before database lock, a Statistical Analysis Plan (SAP) will be prepared to provide full details of all planned analyses. The analyses presented here represent an outline of the intended methodology. Any change to the data analysis methods described in the Clinical Investigation Plan will require an amendment only if it changes a principal feature of the CIP. Any other change to the data analysis methods described in the CIP, and the justification for making the change, will be described in the clinical study report.

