Extended hospitalization	Extended hospital stay or re-hospitalization that is related to the procedure or device that is not: 
 • a planned hospitalization for a pre-existing condition, or procedure required by the Clinical Investigational Plan (including repeat ablation procedure), without serious deterioration in health. • hospitalizations due to recurrent AF/AT/AFL or prolonged hospitalization during the 30 days following procedure to adjust anticoagulation or anti-arrhythmia regimen or to administer diuretic medication.
Effectiveness Evaluation Period	The period between subject's 3-month follow-up visit and 12-month follow-up visit during which the primary effectiveness endpoint will be assessed.
Enrolled Subject	All subjects who sign ICF.
Heart block	Damage to the heart's electrical system that controls heart rhythm.
Hemoptysis	Coughing up blood.
Femoral (groin) hematoma	Bleeding at the catheter insertion site that causes swelling or a pocket of blood. May need to be drained or require additional procedure.
Long Standing Persistent AF	Long-standing persistent AF is defined as continuous AF of greater than 12 months duration.
Myocardial infarction	MI as it relates to AF ablation resulting in the presence of any one of the following criteria: 
 • ECG changes indicative of new ischemia that persist for > 1 hour development of new pathological Q waves on an ECG • imaging evidence of new loss of viable myocardium or new regional wall motion abnormality
Paroxysmal Atrial Fibrillation (PAF)	Recurrent Atrial Fibrillation that last \geq 30 seconds and terminates spontaneously within 7 days.
Pericardial effusion	Accumulation of blood between heart and lining of the heart (pericardium). It is not uncommon to observe "trace" pericardial effusion following AF ablation. Trace effusion that does not need intervention is not considered a serious AE.
Persistent Atrial Fibrillation (PeAF)	Recurrent Atrial Fibrillation that lasts \geq 7 days and does not terminate spontaneously.
Self-Limiting Pericarditis	Pleuritic chest discomfort with or without pericardial rub and ECG changes and did not require additional hospitalization. Generally, not an SAE.
Serious Pericarditis	Pericarditis resulting in an effusion that leads to hemodynamic compromise, requires pericardiocentesis, prolongs hospitalization > 48 hours or persists for more than 30 days following procedure.

DIAMOND-AF II Clinical Investigation Plan

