10.7.4 Three Month Follow-Up Visit

All subjects must be evaluated three-months (90 ± 21 days) following the index ablation procedure.

During this follow-up visit, the following will be performed:

- Perform a limited physical exam (weight, resting heart rate, and blood pressure).
- Assess the subject for any new adverse events and inquire about resolution of any previously reported events(s).
 - Subjects who have experienced symptoms or adverse events suggestive of PV stenosis are required to receive a chest CT or MRI scan to rule out PV stenosis.
- Perform a 12-lead ECG.
 - Report the absence or presence of Atrial Fibrillation or other atrial tachyarrhythmia.
- Record any medication changes.
- Review event monitor data for recordings made due to symptomatic episodes of arrhythmias (if applicable).
- Instruct subject to record twice-monthly 1-minute recordings as well as symptomatic events.
- Subjects will be instructed on how to use the event monitor to capture 24-hour Holter reading and the data will be transmitted remotely to the Corelab.

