10.7.5 Six Month Follow-Up Visit

All subjects must be evaluated six-months (180 ± 28 days) following the index ablation procedure.

During this follow-up visit, the following will be performed:

- Perform a limited physical exam (weight, resting heart rate, and blood pressure).
- Assess the subject for any new adverse events and inquire about resolution of any previously reported events(s).
 - Subjects who have experienced symptoms or adverse events suggestive of PV stenosis are required to receive a chest CT or MRI scan to rule out PV stenosis.
 - Perform a 12-lead ECG.
 - Report the absence or presence of Atrial Fibrillation or other atrial tachyarrhythmia.
- Record any medication changes.
- Review event monitor data for recordings made due to symptomatic episodes of arrhythmias (if applicable) since the last follow-up and the event monitor data from the two (2) required monthly recordings.
- Subjects will be instructed on how to use the event monitor to capture 24-hour Holter reading and the data will be transmitted remotely to the Corelab.
- Administer a follow-up AFEQT Questionnaire (QOL).

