7.9.2 Primary Effectiveness Objective

Primary Effectiveness Objective

To demonstrate that the primary effectiveness rate associated with the DiamondTemp ablation system is higher than the pre-specified Objective Performance Criterion (OPC).

Hypothesis

Revision 1

Page 11 of 18

 H_0 : $P \leq P_0$

 $H_1: P > P_0$

where $P_0 = 40\%$ (Effectiveness OPC), and higher effectiveness rates are better.

Endpoint Definition and Derivation

The primary effectiveness endpoint is defined as freedom from documented Atrial Fibrillation (AF), Atrial Flutter* (AFL) and Atrial Tachycardia (AT) episodes following the blanking period (3-month followup post-ablation procedure) through the end of the effectiveness evaluation period (12-month followup post-ablation procedure).

An effectiveness failure is defined by any of the following events:

- Inability to electrically isolate all accessible targeted pulmonary veins during the ablation procedure.
- Documented episodes of AF, AFL or AT lasting ≥ 30 seconds in duration as evidenced by electrocardiographic data during the effectiveness evaluation period.
- DC cardioversion for AF, AFL or AT during the effectiveness evaluation period.
- A repeat ablation procedure to treat AF, AFL or AT during the effectiveness evaluation period.
- Use of a new or previously failed anti-arrhythmic drug (AAD) at a dose greater than the highest ineffective dose for AF during the effectiveness evaluation period.
- Use of a non-study device for ablation of any AF targets during the index or repeat ablation procedure during the blanking period.
- More than one (1) repeat ablation procedure during the blanking period.

The blanking period for a subject starts on the date of the index ablation procedure (day 0) and ends on day 90 post index ablation.

The effectiveness evaluation period for a subject starts on day 91 post index ablation and ends on the study exit date or day 410 post index ablation (i.e., close of the 12-month visit window), whichever is earlier.

If a primary effectiveness failure event occurs post day 365 and within the effectiveness evaluation period, the date of the event will be set to day 365 so that these events will be accounted for in the 12month Kaplan-Meier estimate of the primary effectiveness endpoint.

Performance Requirements

The null hypothesis will be rejected if the one-sided 97.5% lower confidence bound of the primary effectiveness rate is greater than 40%.

[figure not shown]

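### Under the SAP's day-91 start, an in-window 3-month Holter completed by day 90 cannot count toward the primary effectiveness endpoint, while the Protocol starts that period at the 3-month visit itself

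*Protocol*

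**What the plan says.** **Holter schedule.** Protocol 13.3 has subjects collect a 24-hour Holter with their event monitor "during the 3, 6 and 12 months post-ablation procedure follow-up visit windows". Table 8 (Protocol 10.2) shows the same three recordings.

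**Timing of the first.** Protocol 10.7.4: "All subjects must be evaluated three-months (90 ± 21 days) following the index ablation procedure". At that visit, "Subjects will be instructed on how to use the event monitor to capture 24-hour Holter reading", and the data are sent remotely to the core laboratory. Nothing requires the recording to be on or after day 91.

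**What counts, per the SAP.** SAP 7.9.2 says the blanking period "starts on the date of the index ablation procedure (day 0) and ends on day 90 post index ablation". It continues: "The effectiveness evaluation period for a subject starts on day 91 post index ablation", and ends at study exit or day 410, whichever is earlier. The recurrence criterion is "Documented episodes of AF, AFL or AT lasting ≥ 30 seconds in duration as evidenced by electrocardiographic data during the effectiveness evaluation period".

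**What counts, per the Protocol.** Protocol 2.2 defines the effectiveness evaluation period as "The period between subject's 3-month follow-up visit and 12-month follow-up visit during which the primary effectiveness endpoint will be assessed". The same table describes blanking as the roughly 90-day interval from ablation to the 3-month visit. Table 8 groups the 3-month visit with the 6- and 12-month visits under the effectiveness evaluation period.

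**Next Holter.** Protocol 10.7.5: "All subjects must be evaluated six-months (180 ± 28 days) following the index ablation procedure".

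**The concern.** Table 8 schedules no Holter before the 3-month visit and places that visit in the evaluation period, so the Protocol appears to intend the 3-month Holter as an effectiveness assessment. Under the SAP's fixed start, a subject who is seen and recorded early, fully within the protocol, contributes nothing from that Holter to the primary endpoint. The 12-lead ECG taken at an early visit is lost in the same way.

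The endpoint is documented arrhythmia, in a single-arm trial judged against a fixed 40%. Having two countable Holters instead of three can only leave the number of detected failures equal or lower, and there is no control arm in which the same loss would occur. The SAP deals with the late edge of follow-up by moving events between day 365 and day 410 back to day 365. It has no counterpart for the 3-month window. The tipping-point analysis in SAP 7.4 concerns early dropouts, and the prespecified subgroups are geography, gender and age, so no planned output would show how many Holters could count for each subject.

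**Working it through.** **The plan's own figures.** The documents give no figure for the share of 3-month Holters falling by day 90. The related design figure is 86% power for 49% against 40% with n = 274. A one-sample z-test with null variance gives Φ((0.09 − 1.96·√(0.40·0.60/274)) / √(0.49·0.51/274)) = Φ((0.0900 − 0.0580)/0.0302) = 85.5%. The figure reproduces and does not depend on this point.

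**Step 1: the window.** 90 ± 21 gives days 69-111, which is 43 days. Days 69-90 are 22 of them: 22/43 = 51.2%. A Holter begun on day 90 runs into day 91. If it is treated as countable, the share is 21/43 = 48.8%.

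**Step 2: sensitivity to timing (all assumed).** For normally distributed recording days with mean μ and SD σ, limited to the window:

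share = [Φ((90.5−μ)/σ) − Φ((68.5−μ)/σ)] / [Φ((111.5−μ)/σ) − Φ((68.5−μ)/σ)]

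| Mean day | SD 5 | SD 7 | SD 10 |
|---|---|---|---|
| 85 | 86% | 78% | 70% |
| 90 | 54% | 53% | 52% |
| 95 | 18% | 26% | 34% |
| 100 | 3% | 9% | 20% |

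If visits are uniform over the window but the Holter follows L days later, the share is (22 − L)/43: 49% for L = 1, 44% for L = 3, 35% for L = 7 and 19% for L = 14. This treats recordings that slip past day 111 as countable.

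**Step 3: wait for the first countable Holter.** The 6-month window is 180 ± 28, days 152-208. From day 91 that is 152 − 91 = 61 to 208 − 91 = 117 days (89 at nominal day 180).

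**Step 4: scheduled ambulatory recording time.** Three Holters give 3 × 1,440 = 4,320 minutes. Two 1-minute recordings a month for nine months give 18, for a total of 4,338. Losing one Holter removes 1,440/4,338 = 33%. This measures recording time, not detection probability.

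**Step 5: what it could do to the test (illustration).** Let m be the share of all subjects whose only detectable recurrence would be on the 3-month Holter. Suppose the success rate with all three Holters counting is exactly 40%, and 22/43 of the 3-month Holters do not count, independently of outcome. The observed success rate is then 0.40 + (22/43)·m. With 274 subjects and no censoring, the exact binomial rule needs at least 127 successes.

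| m | Observed success rate | Chance of passing |
|---|---|---|
| 0 | 40.0% | 1.9% |
| 1% | 40.5% | 2.9% |
| 2% | 41.0% | 4.2% |
| 3% | 41.5% | 6.0% |
| 5% | 42.6% | 11.4% |

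The SAP's log-log bound gives the same passing probabilities without censoring. Neither m nor the share 22/43 comes from the documents.

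**The case against.** A reader might infer that about half of subjects lose this Holter. The documents do not support that as a fact. They contain no visit or recording dates, and the visit day need not be the recording day, because subjects are instructed at the visit and transmit remotely. Step 2 shows how far the share moves.

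A reader might also infer that affected subjects are effectively unmonitored until month 6. They are not. Two recordings a month over 61-117 days is about 4 to 8 scheduled checks. Symptomatic recordings and unscheduled visits (Protocol 10.7.8) continue, and cardioversion, repeat ablation and antiarrhythmic drug escalation count as failures from day 91. The 61-117 day wait is also not unusual in this schedule: between the 6-month Holter (days 152-208) and the 12-month Holter (days 320-410) every subject has a gap of 320 − 208 = 112 to 410 − 152 = 258 days.

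The strongest point concerns the estimate itself. Without censoring, a recurrence missed at month 3 but found at any time up to day 410 still counts in the 12-month Kaplan-Meier estimate. Only recurrences that this Holter would have caught and nothing later catches change the rate. The reference value also comes from a consensus statement, and nothing in the documents shows that 40% presumes three countable Holters.

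All of this stands, and it limits the size of the problem. It does not remove the mechanism: an in-window recording completed by day 90 is uncounted under the SAP, and the two documents disagree on when counting starts. Adopting the Protocol's start would largely remove the lost Holter, but blanking would then last anywhere from 69 to 111 days across subjects seen in window. That is a further reason to settle the definition explicitly.

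**Conclusion.** The point holds as a conflict between the Protocol and the SAP with a measurement consequence. Protocol 2.2 and Table 8 tie the start of the evaluation period to the subject's 3-month visit; SAP 7.9.2 fixes it at day 91. Taking the SAP as governing, an in-window recording date decides whether a subject has two or three countable Holters, and affected subjects have their first countable Holter on days 152-208.

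The share affected is about 51% under uniform timing, 52-54% if centred on day 90, and roughly 3-86% under the other timings assumed here. It is lower if the Holter is worn some days after the visit. The direction, compared with counting all three Holters, favours passing the 40% criterion. The size depends on recurrences caught by that Holter alone and never again, which the documents do not give. The passing probabilities in the illustration show sensitivity and are not an estimate of bias. A claim that the reported success rate will be inflated by a known amount goes beyond the documents.

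**What to change.** 1. Reconcile Protocol 2.2 (both period definitions) and Table 8 with SAP 7.9.2 on when the evaluation period starts.
2. In Protocol 10.7.4 and 13.3, keep the 90 ± 21 day visit window but instruct that the 3-month Holter be recorded on or after day 91 (days 91-111). It is already self-recorded and transmitted remotely. A recording made then, after the visit, falls inside the evaluation period under either definition.
3. In the SAP, tabulate the number of subjects with 0, 1, 2 or 3 Holters inside the evaluation period. This replaces the assumed share with an observed one.
4. If the primary rate is shown by presence of a day 91-111 Holter, label it descriptive. Having that Holter is a post-treatment variable that can reflect attendance, dropout or earlier failure, so the comparison is confounded.

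**Cost.** One changed instruction, which may need an amendment and ethics approval under Protocol 16.7 and cannot help subjects already past that visit, and one extra table, which remains possible before database lock. No additional visit or procedure is needed. The observed success rate may be slightly lower.

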14.1 Analysis Populations

Three analysis populations are defined in this study:

- The Intent-to-Treat (ITT) population will be comprised of all subjects who sign ICF and attempt study treatment (i.e. catheter inserted into vasculature).
- The modified ITT (mITT) population will be a subset of the ITT population and comprised of all ITT subjects who meet eligibility criteria.
- The Per-Protocol population will be a subset of the mITT population and comprised of all mITT subjects who do not have any major protocol violations (i.e. eligibility criteria violations, or ablation treatment with a non-study catheter for the index procedure or during blanking period).

14.2 General Aspects of Analysis

The DIAMOND-AF II study will be considered successful when both the primary safety objective and the primary effectiveness objective are met. For each objective, the sample size ensures a power of at least 80% for a one-sided hypothesis test with alpha level of 0.025.

The main analysis of the study objectives will be based on the modified Intent-to-Treat (mITT) population, which includes all subjects who sign informed consent, meet eligibility criteria, and attempt study treatment (i.e. catheter inserted into vasculature). Additionally, sensitivity analyses for the primary objectives will be conducted on the Per-Protocol population, which includes all mITT subjects who do not have any major protocol violations (i.e., eligibility criteria violations, or ablation treatment with a non-study catheter), and the ITT population, which includes all subjects who sign informed consent and attempt study treatment.

The main analysis will include data from all contributing geographies. A poolability analysis will be performed by stratifying analysis of the primary objectives by geographical region and reporting results separately for each region. Similarly, poolability by age and gender will be assessed.

The subjects' baseline characteristics will be summarized for the mITT population with standard descriptive summary statistics, including counts and percentages for categorical variables, and mean, standard deviation, median, quartiles and range for continuous variables. Ordinal variables may be analyzed as if they were continuously scaled. Treatment characteristics and safety data will be summarized for the mITT population.

For the ITT population, subject disposition will be illustrated in a study flow diagram, and subject attrition will be identified and summarized. Subject visits will be tabulated and compliance to visit schedule will be summarized for the mITT population.

For each of the objectives the available data will be summarized. The main analysis of the study objectives will be based on available data and missing data will not be imputed. For the primary safety and effectiveness objectives, a tipping point analysis will be performed to assess the potential impact of missing data.

